16. SAFETY OUTCOMES

There will be no statistical comparisons between the treatment groups for safety data, unless otherwise specified with the relevant section.

16.1. ADVERSE EVENTS

The analysis of solicited adverse event will be performed in the Solicited Safety Set. The percentage of participants with at least 1 administration site AE (solicited and unsolicited), with at least 1 systemic AE (solicited and unsolicited) and with any AE during the 7-day or the 28-day follow-up period, for each step, will be tabulated with exact 95% CI after each vaccination and overall. The same calculations will be performed for symptoms rated as grade 3 (severe). This combined analysis of solicited and unsolicited AEs will be performed on the Exposed Set as requested for public disclosure. Solicited events and unsolicited AEs will be coded by MedDRA.

The percentage of doses followed by at least 1 administration site AE and by at least 1 systemic AE will be tabulated, overall vaccination course, with exact 95% CI. The same computations will be done for Grade 3 AEs, any AEs considered related to vaccination, any Grade 3 AEs considered related to vaccination and any AEs resulting in a medically attended visit.

The percentage of participants/doses reporting each individual solicited administration site and systemic AE during the 7-day follow-up period will be tabulated with exact 95% CI as follows:

- Over the 2 doses, the percentage of participants with the symptom and its exact 95% CI.
- Over the 2 doses, the percentage of doses with the symptom and its exact 95% CI.
- At each study dose (visit), the percentage of participants with the symptom and its exact 95% CI.

Percentage of participants with at least one fever event will be reported per grade (as per protocol scale) and per 0.5°C cumulative increments as from $\geq 38^{\circ}\text{C}$ to $\geq 40^{\circ}\text{C}$

Solicited events ongoing after the observation period reported by maximum intensity will be left out of summary tables and only reported in solicited AE listings. Any solicited event with onset day greater than solicited period (i.e., 7 days) will be reported as unsolicited AE and will be included in unsolicited summary tables and listings.

The analysis of unsolicited adverse event will be performed in the Unsolicited Safety Set. The verbatim reports of unsolicited symptoms will be reviewed by a physician and the signs and symptoms will be coded per the Medical Dictionary for Regulatory Activities (MedDRA), Version 25.0. Every verbatim term will be matched with the appropriate preferred term (PT). The percentage of participants with unsolicited AEs within 28 days after any doses with its exact 95% CI will be tabulated by group, step and by MedDRA preferred term. Similar tabulation will be done for Grade 3 unsolicited AEs, for unsolicited AEs that resulted in a medically attended visit, for Grade 3 and causally related unsolicited

Document: \\dccar2dnetvnasc01p-lan1.quintiles.net\cp_ops\PROJECTS\Glaxo SmithKline\GSK205480_HAB61752\SAP
Author: PPD Version Number: 1.0
Version Date: 25OCT2022

Template No: CS_TP_BS016 – Revision 7
Effective Date: 01Nov2021

Reference: CS_WI_BS005

AEs and for unsolicited AEs causally related to vaccination. These tabulations will include System Organ Class (SOC) and SOC/PT analyses.

The number of participants who experienced at least 1 SAE after any dose, from dose 1 until 28 days post second dose (Day 197) and from Day 198 until Day 337 will be reported by treatment.

The following summaries for COVID-19 infections will be presented:

- Number of participants with an AE of suspected, probable or confirmed assessment of COVID-19 infection
- Number of participants who had a COVID-19 diagnosis test performed and the number of participants with positive, negative or indeterminate results
- Incidence of COVID-19 as AEs and SAEs

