4. STUDY DESIGN

4.1. Overall design

This is a Phase 1 observer-blind, controlled, self-contained, randomised, single-centre, dose-escalation study with 3 Steps (Step 1a, Step 1b, and Step 2). A total of 96 participants in 7 study groups, including 17 sentinel participants, are planned to be enrolled in the study. [Figure 1](#) shows a visual representation of the study design and [Table 4](#) shows a description of the study intervention groups.

An electronic case report form (eCRF) and a paper Diary will be used for data collection, which will include biological sampling (blood) and safety follow-ups.

The study design, the enrolment, and the monitoring procedures will follow GSK safety standards for FTIH clinical studies (Refer to Sections [8.2.2](#) and [10.1.5](#) for details on staggered vaccination, safety monitoring, and holding rules).

The primary completion date will be at Visit 6 (Day 197), 28 days after administration of the second study intervention (booster vaccination). An extended safety follow-up will be performed until 6 months after this second study intervention administration (Day 337) for collection of SAEs.

Figure 1 Study design overview

[figure not shown]

Table 4 Study groups, intervention, and blinding

Study groups	Number of participants	Age (Min-Max)	Study intervention(s)	Blinding	
				FSFV → IA 1*	IA 1* → LSLV)
Step 1a low dose without Alum	12	18 – 50 years	2 intramuscular vaccinations (Day 1 and Day 169) with low dose of Vi-CRM ₁₉₇ +O:2-CRM ₁₉₇ without Alum	Observer-blind	Single-blind*
Step 1a control	6		1 intramuscular vaccination (Day 1) with TYPHIM VI and 1 intramuscular vaccination (Day 169) with CCI [REDACTED]		
Step 1b low dose with Alum	12		2 intramuscular vaccinations (Day 1 and Day 169) with low dose of ADJ+Vi-CRM ₁₉₇ +O:2-CRM ₁₉₇ with Alum		
Step 1b control	6		1 intramuscular vaccination (Day 1) with TYPHIM VI and 1 intramuscular vaccination (Day 169) with CCI [REDACTED]		
Step 2 full dose without Alum	24		2 intramuscular vaccinations (Day 1 and Day 169) with full dose of Vi-CRM ₁₉₇ +O:2-CRM ₁₉₇ without Alum		
Step 2 full dose with Alum	24		2 intramuscular vaccinations (Day 1 and Day 169) with full dose of ADJ+Vi-CRM ₁₉₇ +O:2-CRM ₁₉₇ with Alum		
Step 2 control	12		1 intramuscular vaccination (Day 1) with TYPHIM VI and 1 intramuscular vaccination (Day 169) with CCI [REDACTED]		

FSFV = first subject first visit; IA = interim analysis; LSLV = last subject last visit

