3. STUDY DESIGN

3.1. GENERAL DESCRIPTION

This is a Phase 1 observer-blind, controlled, self-contained, randomised, single-centre, dose-escalation study with 3 steps (Step 1a, Step 1b, and Step 2). A total of 96 participants in 7 study groups, including 17 sentinel participants, are planned to be enrolled in the study.

The target will be to enroll approximately 96 eligible participants, 18 to 50 years of age, who will be randomly assigned to the different study groups, according to Step:

Step 1a: 18 adults will be assigned in a 2:1 ratio to the following study groups

- “Step 1a low dose without Alum” (approximately 12 participants)
- “Step 1a control” (approximately 6 participants)

Step 1b: 18 adults will be assigned in a 2:1 ratio to the following study groups

- “Step 1b low dose with Alum” (approximately 12 participants)
- “Step 1b control” (approximately 6 participants)

Step 2: 60 adults will be assigned in a 2:2:1 ratio to the following study groups

- “Step 2 full dose without Alum” (approximately 24 participants)
- “Step 2 full dose with Alum” (approximately 24 participants)
- “Step 2 control” (approximately 12 participants)

The investigational vaccines, Vi-CRM₁₉₇ + O:2-CRM₁₉₇ and ADJ+Vi-CRM₁₉₇ + O:2-CRM₁₉₇, will be administered in 2 different doses depending on Step. The low dose will be administered by fractional dosing (0.1 mL) retrieved from the same 0.5 mL vial presentation as the full dose. The licensed vaccines (controls), TYPHIM VI and **CCI** will be administered as per their SmPC.

Step 1a:

A “lower dose without Alum” subgroup comprised of 2 study groups (2:1 randomisation [Step 1a low dose without Alum: Step 1a control]) will receive either 2 vaccinations with the candidate low dose Vi-CRM₁₉₇+O:2-CRM₁₉₇ vaccine without Alum (on Day 1 and Day 169) or 1 vaccination with the TYPHIM VI vaccine on Day 1 (as control for the first vaccination) and 1 vaccination with the **CCI** vaccine on Day 169 (as control for the second vaccination).

First, 6 sentinel participants will receive, on consecutive days, either the low dose of the Vi-CRM₁₉₇+O:2-CRM₁₉₇ or the TYPHIM VI vaccine (2:1 randomisation). Each sentinel participant will be followed up with a safety phone call approximately 1 day after vaccination. If there are any safety concerns, the sentinel participant will be asked to visit the site to assess any potential SAEs or to assess

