6.1. SUMMARY STATISTICS

For qualitative variables, the population size (N for sample size and n for available data) and the percentage (of available data) for each class of the variable will be presented. Quantitative variables will be summarized using descriptive statistics, including N (with data available), mean, standard deviation (SD), coefficient of variation (CV%), median, Q1, Q3, minimum, and/or maximum values. Geometric mean will be included for immunogenicity parameters, where applicable. Coefficient of variation will not be presented for change from baseline results.

The exact two-sided 95% CIs for a proportion within a group will be calculated using the Clopper-Pearson exact method.

The geometric mean antibody concentrations (GMCs) and CCI [REDACTED] calculations will be performed by taking the anti-log of the mean of the log10 titer transformations. Confidence interval for geometric means will be derived by raising 10 to the confidence interval associated with mean of log10 values i.e., CI of geometric mean = $10^{(CI \text{ for the mean of log10 values})}$. All participants with valid data will be considered. Participants whose antibody titers are below the cut-off of the assay will be given an arbitrary value of half the cut-off for the purpose of GMC/CCI [REDACTED] calculation.

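### SAP 16.1 puts Clopper-Pearson intervals on percentages of doses and ignores that a participant gives two; if those doses are positively correlated, intervals for common events are too narrow, and control rows mix two vaccines

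*SAP*

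**What the plan says.** SAP 16.1 uses the dose as the unit of analysis in two places.

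- Any AE, solicited or unsolicited: "The percentage of doses followed by at least 1 administration site AE and by at least 1 systemic AE will be tabulated", over the whole vaccination course with an exact 95% interval. The same is planned for Grade 3, related, Grade 3 related and medically attended AEs.
- Each solicited symptom: "Over the 2 doses, the percentage of doses with the symptom and its exact 95% CI".

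SAP 6.1 fixes the method: "The exact two-sided 95% CIs for a proportion within a group will be calculated using the Clopper-Pearson exact method". Neither section mentions clustering by participant.

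Protocol 4.1, Table 4, gives each investigational group the same formulation on Day 1 and Day 169. Each control group gets "1 intramuscular vaccination (Day 1) with TYPHIM VI and 1 intramuscular vaccination (Day 169) with" a second product. Its name is redacted, but Protocol 2.2 describes it as a tetanus, diphtheria and pertussis booster.

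SAP 16.1 also plans participant-level percentages with exact intervals: each solicited symptom at each dose, and any and Grade 3 AEs after each vaccination and overall.

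**The concern.** Clopper-Pearson limits are exact only for independent Bernoulli observations. A group of 24 participants gives up to 48 doses but only 24 independent people. If someone who reacts to the first dose is more likely to react to the second, 48 doses carry less information than 48 people would, and the interval is too short for its label. Positive correlation is plausible when the same vaccine is given twice, and the SAP does allow for repeated measures within a participant in its immunogenicity model (SAP 15).

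The control rows raise a separate question that does not depend on correlation. Investigational groups receive one product twice, whereas control groups receive two products once each. A per-dose control percentage is therefore not the rate for either comparator, and it is not like for like with the investigational rows beside it.

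At stake is how precisely per-dose reactogenicity appears to be known, and whether the control row can serve as a reference.

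**Working it through.** **Inputs.** Group sizes from SAP 3.1 and Protocol Table 4: 24 in each Step 2 full-dose group; 12 in each low-dose group and in the Step 2 control group; 6 in each Step 1 control group. Two doses each, assuming everyone receives both. Interval method from SAP 6.1. The correlation rho is an assumption, shown from 0 to 1.

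**Reproducing the plan's own figures.** The documents print no per-dose interval. They do print Clopper-Pearson limits in Protocol Table 15 (n = 21). All nine rows reproduce; for example 10/21 gives 25.7% to 70.2%.

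**Model.** With event rate p at both doses, each participant has:

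- both doses with the event: p² + rho·p(1−p)
- exactly one: 2p(1−p)(1−rho)
- neither: (1−p)² + rho·p(1−p)

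Summing over n participants (by convolution) gives the exact distribution of the dose count X. Coverage is the probability that X takes a value whose Clopper-Pearson interval on 2n doses contains p. The variance of X is 2n·p(1−p)(1+rho), so the standard error is understated by √(1+rho): 1.14 at rho 0.3, 1.22 at 0.5, 1.41 at 1.

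**Hand check, n = 24, p = 50%.** The interval covers 50% when X is 17 to 31, that is 24 ± 7. At rho 0 the SD is √(48 × 0.25) = 3.46, and 7.5/3.46 = 2.17 gives about 97.0% (exact 97.1%). At rho 0.5 the SD is √18 = 4.24, and 7.5/4.24 = 1.77 gives about 92.3% (exact 92.4%).

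**Exact coverage of the nominal 95% interval.**

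| Participants (doses) | rho | rate 20% | rate 30% | rate 50% |
|---|---|---|---|---|
| 24 (48) | 0 | 95.4% | 97.4% | 97.1% |
| | 0.3 | 91.9% | 94.9% | 94.3% |
| | 0.5 | 89.5% | 93.0% | 92.4% |
| | 1 | 79.6% | 88.3% | 84.8% |
| 12 (24) | 0.3 | 96.3% | 95.2% | 95.3% |
| | 0.5 | 94.6% | 93.3% | 93.5% |
| | 1 | 85.9% | 87.6% | 85.4% |
| 6 (12) | 0.3 | 96.3% | 95.0% | 92.7% |
| | 0.5 | 95.2% | 92.6% | 90.2% |
| | 1 | 90.1% | 81.2% | 78.1% |

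Clopper-Pearson is conservative to begin with, which absorbs part of the effect. Averaged over event rates from 5% to 95%, coverage falls below 95% from about rho 0.2 (n = 24), 0.3 (n = 12) and 0.5 (n = 6). The n = 6 rows are illustrative: those groups are all controls, whose two doses are different vaccines.

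**Uncommon events.** At a 5% rate the lowest coverage over rho 0 to 1 is 96.4% (n = 24), 97.6% (n = 12) and 95.7% (n = 6). At a 10% rate with n = 24 it is 95.1% at rho 0.3 and 93.2% at rho 0.5.

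**Width, 24 events in 48 doses.** The planned interval is 35.2% to 64.8% (29.5 points). On the effective number of doses, 48/(1+0.5) = 32, it is 31.9% to 68.1% (36.2 points). The planned width is 29.5/36.2, about 82% of that.

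**Control groups with unequal rates.** Suppose TYPHIM VI and the booster have rates of 30% and 70%. The per-dose row then estimates 50%, which is neither. At rho 0.3 its interval covers that 50% with probability 95.2% (n = 6), 97.1% (n = 12) and 96.3% (n = 24, all controls pooled as SAP 6.2 allows). With rates of 40% and 70% the figures are 97.2%, 96.4% and 93.9%. Coverage can fall on either side of 95%.

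**The case against.** The strongest reply is that little depends on these intervals. The primary safety endpoints are percentages of participants (Protocol 3 and 9.4.1), and the holding rules count participants (Protocol 8.2.2.3, Table 11). No hypothesis is tested (Protocol 9.1), and SAP 16 plans no between-group safety comparison by default. The per-visit symptom rows already separate the two control vaccines, because at each visit a control group received one product. All of this stands.

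It also stands that under-coverage is conditional. A reader might infer that every per-dose interval is too narrow. The documents do not support that: they give no correlation, five of the seven groups have 12 or fewer participants, and uncommon events keep at least 95% coverage. It is therefore not shown that the Grade 3, related or medically attended rows under-cover, since such events may be rare. Nor is under-coverage shown for controls.

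Two things survive. An interval labelled exact 95% rests on an independence assumption that the design does not satisfy, and calling the table descriptive does not repair the label. And the by-vaccination rows do not cover everything. For solicited and unsolicited AEs combined, SAP 16.1 plans the related, Grade 3 related and medically attended summaries only per dose over the whole course. The participant-level versions cover unsolicited AEs only, after any dose. For those categories no planned summary separates TYPHIM VI from the booster.

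**Conclusion.** The point holds in a conditional form. The per-dose intervals use a method that ignores the pairing of doses within participants. Given positive correlation and a common event, they are too narrow, most clearly in the two full-dose groups: 89.5% to 93.0% coverage at rho 0.5 for rates of 20% to 50%, and 79.6% to 88.3% in the extreme case of rho 1. On average the smaller groups are less affected at moderate rho, though not at every rate. These figures rest on an assumed rho, equal rates at both doses and full attendance; participants with only one dose would weaken the effect.

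The control-row point needs no such assumption: the percentage averages two different vaccines and describes neither.

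It would be tempting to read this as a threat to the trial's primary safety objective. It is not, because every primary safety endpoint is a participant-level percentage and is untouched. This is a defect in supplementary descriptive tables that is worth correcting because the correction is cheap.

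**What to change.** In SAP 16.1:

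1. Drop the confidence interval from all percentages of doses. Keep the percentages if wanted, and rely for precision on the participant-level rows by vaccination, which already carry exact intervals.
2. If a per-dose interval is kept, use one that treats the participant as the cluster and does not collapse when there are no events. One option is exact limits on 2n/(1+rho) doses, with rho fixed in advance. A participant-level bootstrap is unsuitable: with zero events it returns a zero-width interval, and rho cannot be estimated from such a row.
3. For control groups, report dose 1 (TYPHIM VI) and dose 2 (the booster) separately, with no pooled dose row. Include the related, Grade 3 related and medically attended categories. SAP 6.4.1 already attributes each event to a dose, so no new data are needed.

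The cost is SAP wording, minor programming, and per-dose intervals that are wider or absent. No endpoint, data collection or sample size changes.

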3. OBJECTIVES AND ENDPOINTS

Table 3 Study objectives and endpoints (Amended, 21 August 2023)

Objectives	Endpoints
	Primary
Evaluate the safety profile of the Vi-CRM ₁₉₇ +O:2-CRM ₁₉₇ vaccine, with and without adjuvant.	
 • Percentage of participants with solicited administration-site events during 7 days after each vaccination, on the days of vaccination and the 6 subsequent days (study intervention administered on Day 1 and Day 169), per study group. • Percentage of participants with solicited systemic events during 7 days after each vaccination, on the days of vaccination and the 6 subsequent days (study intervention administered on Day 1 and Day 169), per study group. • Percentage of participants with unsolicited adverse events (AE) during 28 days after each vaccination, on the days of vaccination and 27 subsequent days (study intervention administered on Day 1 and Day 169), per study group. • Percentage of participants with any serious adverse event (SAE) from first vaccination until 28 days after second study intervention administration (Day 1 to Day 197), per study group. • Percentage of participants with AEs/SAEs leading to withdrawal from the study or withholding further study intervention administration, from first study intervention administration until 28 days after second study intervention administration (Day 1 to Day 197), per study group. • Percentage of participants with deviations from normal or baseline[†] values of haematological, renal, and hepatic panel test results at 7 days after each vaccination (Day 8 and Day 176), per study group.
	Secondary
Evaluate the long-term safety profile of the Vi-CRM ₁₉₇ +O:2-CRM ₁₉₇ vaccine, with and without adjuvant.	
 • Percentage of participants with any SAE from 28 days after second vaccination (Day 197) up to Day 337, per study group. • Percentage of participants with AEs/SAEs leading to withdrawal from the study from 28 days after second vaccination (Day 197) up to Day 337, per study group.

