9.4. Statistical analyses

9.4.1. Primary endpoint(s) (Amended, 21 August 2023)

[figure not shown]
Endpoint description	Analysis set	Statistical analysis methods
• Percentage of participants with solicited administration-site events during 7 days after each vaccination, on the days of vaccination and the 6 subsequent days (study intervention administered on Day 1 and Day 169), per study group	Solicited Safety Set	• Number and percentages of participants with at least one, any, and Grade 3 administration-site solicited AEs
• Percentage of participants with solicited systemic events during 7 days after each vaccination, on the days of vaccination and the 6 subsequent days (study intervention administered on Day 1 and Day 169), per study group	Solicited Safety Set	• Number and percentages of participants with at least one, any, and Grade 3 systemic solicited AEs
• Percentage of participants with unsolicited AEs during 28 days after each vaccination, on the days of vaccination and 27 subsequent days (study intervention administered on Day 1 and Day 169), per study group	Unsolicited Safety Set	• Number and percentages of participants with unsolicited AEs
• Percentage of participants with any SAEs from first vaccination until 28 days after second study intervention administration (Day 1 to Day 197), per study group	Exposed Set	• Number and percentages of participants with SAEs
• Percentage of participants with AEs leading to withdrawal from the study or withholding further study intervention administration, from first study intervention administration until 28 days after second study intervention administration (Day 1 to Day 197), per study group	Exposed Set	• Number and percentage of participants with AEs/SAEs leading to withdrawal from the study or withholding further study intervention administration
• Percentage of participants with deviations from normal or baseline t values of haematological, renal, and hepatic panel test results at 7 days after each vaccination Day 8 and Day 176 per study group*	Exposed Set	• Number and percentages of participants having haematological, renal, and hepatic abnormalities

[†]Baseline for post-first vaccination at Day 8 is Day 1 (can also be screening blood draw, if performed within 3 days of first vaccination), and baseline for post-second vaccination at Day 176 is Day 169.

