9.5.1. Sequence of analyses

A first interim analysis on safety and immunogenicity will be performed by a Sponsor's delegate unblinded statistician on data collected from all participants until 28 days after the first vaccination in Step 2 (Visit 3, Day 29). An interim CSR will be produced but no individual listings will be generated. Results will not impact the continuation of the study itself but will inform further development of the candidate vaccine in other studies. Since some treatment groups of specific participants may be revealed during the interim analysis, the study will be considered single-blind from this point and onwards with the Investigator, site staff and participants remaining blinded up to EoS.

A second interim analysis on safety and immunogenicity may be performed by a Sponsor's delegate unblinded statistician on data collected from all participants until 28 days after the second vaccination in Step 2 (Visit 6, Day 197). No individual listings will be generated.

The final analysis will include all data for at least primary and secondary endpoints up to and including follow-up safety phone contact (Day 337). **CC1**
CC2 A final CSR containing all available data will be written and made available to the investigators.

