7.1.3. ADVERSE EVENTS

Solicited Adverse Events:

Daily recording of solicited adverse events: for diary cards indicating the presence or absence of solicited adverse events, for studies using paper diaries which have questions in the CRF indicating the presence or absence of solicited events the following rules are applicable:

- Denominators for the summary of administration site (or systemic) solicited adverse events will be calculated using the number of participants who respond "Yes" or "No" to the question concerning the occurrence of administration site (or systemic) adverse events.
- When a specific solicited adverse event is marked as having not occurred following a specific vaccination (i.e., SDTM FA.FAOCCUR=N for the specified post-vaccination period for the adverse event in question), all daily measurements will be imputed as Grade 0.
- When a specific solicited adverse event is marked as having occurred following a specific vaccination (i.e., SDTM FA.FAOCCUR=Y for the specified post-vaccination period for the adverse event in question), any missing daily recordings will be given imputed values to allow them to contribute to the 'Any' rows but not to specific grade rows of the solicited adverse event summary tables.
- When the occurrence of a specific solicited adverse event is not present (i.e. SDTM FA.FAOCCUR is neither Y nor N for the specified post-vaccination period for the symptom in question) but the group of solicited adverse events (administration site or systemic) is marked as having occurred (i.e. SDTM FA.FAOCCUR=Y), all missing daily recordings will be given imputed values to allow them to contribute to the 'Any' rows but not to specific grade rows of the solicited adverse event summary tables.

The following table shows how participants contribute to each category for a specific solicited adverse event over the Day X to Day Y post-vaccination period:

Document:	\dccar2dnetvnasc01p-lan1.quintiles.net\cp_ops\PROJECTS\Glaxo SmithKline\GSK205480_HAB61752\SAP		
Author:	PPD	Version Number:	1.0

Template No: CS_TP_BS016 – Revision 7
Effective Date: 01Nov2021

Reference: CS_WI_BS005

Solicited adverse event category	Participants included in the calculation of the numerator
Any	All participants with at least one occurrence of the adverse event at grade 1, grade 2, or grade 3 between Day X and Day Y or with the adverse event marked as present and at least one missing daily recording between Day X and Day Y

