7.2.4. DURATION OF EVENTS

The duration of an event with a start and end date will be the number of days between the start and end dates plus one day, i.e., an event that starts on 03MAR2018 and ends on 12MAR2018 has a duration of 10 days.

The duration of solicited events will be calculated as the difference between the dates when the first and last symptom reported at grade 1 or higher were observed plus one day (also including days after Day 7 if event is still ongoing).

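### SAP 16.1 can be read as dropping solicited events that continue past Day 7 from the primary safety tables, against the protocol endpoints and the SAP's own counting rules

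*SAP*

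**What the plan says.** The two reactogenicity endpoints in Protocol Section 3 (Table 3) are participant-level percentages over a seven-day window. The first reads "Percentage of participants with solicited administration-site events during 7 days after each vaccination, on the days of vaccination and the 6 subsequent days"; the systemic endpoint has the same form. Protocol 9.4.1 gives the methods as "Number and percentages of participants with at least one, any, and Grade 3 administration-site solicited AEs" and "Number and percentages of participants with at least one, any, and Grade 3 systemic solicited AEs". Neither section sets an event aside because it outlasts the window.

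The SAP has two general counting rules. Section 7.1.3 builds the any-grade numerator from "All participants with at least one occurrence of the adverse event at grade 1, grade 2, or grade 3 between Day X and Day Y", plus participants with the event marked present and a daily recording missing, and gives a matching row for each grade. Section 7.2.6 keeps participants with a documented symptom and classifies them by their highest daily grade in the solicited period. Section 16.1 then plans a table of each solicited symptom over the 7-day follow-up.

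Later in 16.1 comes the sentence at issue: "Solicited events ongoing after the observation period reported by maximum intensity will be left out of summary tables". It goes on to confine them to the listings of solicited events. The sentence after it sends solicited symptoms with onset after Day 7 to the unsolicited tables. SAP 7.2.4 calculates the duration of solicited events, "also including days after Day 7 if event is still ongoing". SAP 3.3 declares no change from the protocol's analyses.

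For the first interim, Protocol 9.5.1 says: "An interim CSR will be produced but no individual listings will be generated". SAP 4.3 likewise plans no individual listings there.

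**The concern.** The grammatical subject of the 16.1 sentence is the events, not the days or grades recorded after Day 7. Followed as written, it makes inclusion in a primary safety numerator depend on the outcome: the longer a reaction lasts, the more likely it is to be left out. That biases the any-grade and Grade 3 percentages downward, and by different amounts if one formulation gives longer reactions than another.

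The sentence also sits in the adverse-event analysis section and names exactly this case. A programmer could reasonably treat it as a specific exception to the general rules in 7.1.3 and 7.2.6. Another could follow the general rules. The choice should be settled before anyone sees results by group.

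**Working it through.** **Step 1. One test case against each rule.** Take swelling that starts on Day 2 and is still present on Day 8.

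| Text | Counted in the Day 1–7 tables? |
|---|---|
| Protocol Table 3 and 9.4.1 | Yes; present in the window |
| SAP 7.1.3 | Yes; in the any-grade row and each grade recorded in the window |
| SAP 7.2.6 | Yes; at its highest grade in the window |
| SAP 16.1, 7-day tabulation | Yes |
| SAP 16.1, ongoing-event sentence read literally | No; listings only |
| SAP 16.1, late-onset sentence | Does not apply; onset is Day 2, so the unsolicited tables do not recover it |
| SAP 7.2.4 | Not a counting rule; days after Day 7 enter the duration |

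The conflict is with the protocol endpoints, 7.1.3, 7.2.6 and the tabulation in 16.1 itself. Section 7.2.4 shows only that time after Day 7 is expected to be recorded, which fits either reading.

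**Step 2. The plan's own safety figure.** Protocol Table 14 gives the probability of at least one event as 1 − (1 − p)^n.
- n = 24, p = 7.5%: 1 − 0.925^24 = 84.6%, as printed.
- n = 12, p = 15%: 1 − 0.85^12 = 85.8%, as printed.

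All 18 entries reproduce, so Table 14 is not in question.

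**Step 3. Size under the literal reading.** A dropped event leaves the numerator. The denominator stays, because SAP 7.1.3 takes it from participants who answered the occurrence question. One participant lost is 1/12 = 8.3 points or 1/24 = 4.2 points.

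The documents give no persistence rate, so the counts below are assumed. They refer to participants with no other solicited event of that type to keep them in the numerator. Intervals are exact 95% (Clopper-Pearson).

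| Participants lost | Starting from 6/24 | Starting from 3/12 |
|---|---|---|
| 0 | 25.0% (9.8–46.7) | 25.0% (5.5–57.2) |
| 1 | 20.8% (7.1–42.2) | 16.7% (2.1–48.4) |
| 2 | 16.7% (4.7–37.4) | 8.3% (0.2–38.5) |
| 3 | 12.5% (2.7–32.4) | 0% (0–26.5) |

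On the Table 14 scale, if a share f of events is dropped, the probability of tabulating at least one is 1 − (1 − p(1 − f))^n. For f = 10%, 25% and 50% (assumed):
- n = 24, p = 7.5%: 84.6% falls to 81.3%, 75.1% and 60.0%.
- n = 12, p = 15%: 85.8% falls to 82.5%, 76.1% and 60.8%.

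**Step 4. Size under 7.1.3 and 7.2.6.** Zero. The participant is counted whether or not the event continues.

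**Step 5. The first interim.** Under the literal reading, a continuing event is in neither the solicited tables nor a listing. Under the narrower reading, its Day 1–7 part is tabulated and only the continuation is missing. In both cases persistence itself goes unreported there: 7.2.4 derives a duration, but 16.1 describes no summary of duration or of ongoing events.

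**The case against.** The best defence is that the sentence was never meant to remove anyone from the endpoints. Events on Days 1–7 are captured as daily recordings, so the words about maximum intensity plausibly describe a separate record for the time after Day 7, to be listed and not tabulated. That reading agrees with 7.1.3, 7.2.6, the 7-day tabulation in 16.1 and the statement in SAP 3.3. SAP Section 8 also says that table content is set by templates supplied with the plan. These are not in the documents reviewed here and might settle the matter.

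Much of this stands. A reader might infer that the SAP definitely removes the most persistent reactions from two primary endpoints. The documents do not support that; it is the literal result of one sentence that other sections contradict.

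A reader might also infer that such reactions would be seen nowhere at the first interim. That goes too far as well. The iSRC's unblinded Safety evaluation #3 covers all available safety data to 28 days after first vaccination in Step 2 (Protocol 8.2.2.1). Holding rules 2a and 2b separately count Grade 3 solicited events lasting 48 hours or more. Any gap is confined to the interim analysis and its CSR.

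Finally, single-symptom counts do not carry over to the endpoints, which count participants with at least one event of a type. A participant with persistent swelling and pain that resolved within the window still counts as having an administration-site event.

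What the defence does not supply is text. The narrower reading has to be inferred, and the sentence as written says something else.

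**Conclusion.** The SAP gives two incompatible instructions for the numerators of two primary safety endpoints. The literal instruction in 16.1 departs from the protocol and lowers rates in a way that depends on how long the reaction lasts. Whether it would be applied cannot be told from the documents.

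The effect is 8.3 points (n = 12) or 4.2 points (n = 24) for each participant whose only solicited events of that type are ongoing after Day 7, or nothing if 7.1.3 and 7.2.6 are followed. How many such participants to expect is unknown. The analyses are descriptive, so no test or error rate is affected. What is at stake is the accuracy and reproducibility of the reported reactogenicity, including in an interim CSR that has no listings behind its tables.

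**What to change.** Replace the sentence in SAP 16.1 with:

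> Solicited events with onset on Days 1–7 are included in all solicited summary tables, graded by the maximum intensity recorded on Days 1–7, whether or not they are ongoing after Day 7. Only intensity recorded after Day 7 is excluded from grading and listed.

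Optionally, add one row giving the number and percentage of participants, per group and dose, with a solicited event ongoing after Day 7. No endpoint requires it, but it would show persistence at the first interim. It may also help at the second, where SAP 4.3 plans individual listings and Protocol 9.5.1 rules them out.

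The cost is one sentence and, if wanted, one table row; no new data are needed. If the narrower reading was intended, the edit only records it. If the literal one was, reported rates may rise. The change should be made before any unblinded table is run. If tables already exist, confirm which rule the programs used.
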